**If you had the choice between these two medications for thyroid replacement therapy, which one would you choose?**

- a. once-daily oral pill
- b. once-weekly injection
- c. no preference

**If you prefer one of the administration methods, how strong is the preference?**

- a. Very strong
- b. Fairly strong
- c. Slightly strong
- d. Not very strong

**If you prefer one of the administration methods, what are the main reason(s) for your preference? Choose all that apply.**

- a. Convenience
- b. Ease of administration
- c. Frequency of administration
- d. My level of compliance with therapy
- e. Confidence in my therapy
- f. Other

**APPENDIX E. MODIFIED DRAIZE SCALE**

## Draize Scales

g. *Study Personnel Instructions:* The Modified Draize Scale as shown in the table below will be used for physical examination/rating of abnormalities at the injection site.

h. The injection site should be examined by the Investigator/qualified designee for formation of both erythema and edema and results recorded in the eCRF at the timepoint noted in the Schedule of Assessments.

i. If the Draize score is >1 at 30 minutes, the subject will be discharged, and a follow up visit will be scheduled at 24 ( $\pm 3$ ) hrs post-dose to allow the Investigator or designee to complete an assessment of the injection site using the Modified Draize Scale.

Erythema Formation		Edema Formation	
Description	Score	Description	Score
No erythema	0	No edema	0
Very slight erythema Barely perceptible	1	Very slight edema Barely perceptible	1
Slight erythema (Edges of area well defined by definite raising)	2	Slight edema (Edges of area well defined by definite raising)	2
Moderate erythema	3	Moderate edema Raised approx. 1 mm	3
Severe erythema Beet redness to slight eschar formation	4	Severe edema Raised more than 1 mm and beyond exposure area	4

Source: [FDA, 1999](#); [Draize et al, 1944](#)

**APPENDIX F. SUMMARY OF PRIOR CHANGES TO PROTOCOL****Rationale and Summary of Changes from Protocol Version 1.0 to Version 2.0**

This protocol was amended to update the minimum current daily dose of oral levothyroxine permitted for enrollment into the study to a level that would permit subjects to start at a dose of 100 µg XP-8121. The minimum laboratory values for hematocrit and hemoglobin were also updated to reflect the lower limit of the normal range for the central laboratory being used for the study. In the preparation of this amendment, other minor updates were made and are included in the following table.

Affected Sections/Tables	Summary of Revisions Made	Rationale
General	Minor formatting updates and clarifications. Updated wording to increase specificity of procedures and timing.	Administrative update.
Section 1	Added new protocol version.	Administrative update.
Summary of Revisions	Added description of changes made to the protocol with the amendment.	Administrative update.
Procedures in Case of Emergency	Removed reference to direct phone number.	Administrative update.
Section 2	Synopsis was updated to align with changes in main body of protocol.	Administrative update.
Table 2	Removed study procedure for oral levothyroxine administration during Screening and at the End of Maintenance Visit.	Oral levothyroxine administration is part of the eligibility assessments performed during the Screening Period and at the End of Maintenance it is a return to standard of care for the subject.
Table 2	Moved clinical safety laboratory assessment from the end of the Titration Period to the beginning of the Maintenance Period.	Clarified timing of clinical safety laboratory assessment from the end of the Titration Period, as it is unknown at the time of the visit if it is the last visit in the Titration Period; therefore, the laboratory assessments for this need to be performed at the beginning of the Maintenance Period.
Table 2	Clarified timing of urine pregnancy test during Titration Period as Weeks 1, 3, 5 and 7.	Administrative update.
Table 2	ECG footnote updated to include handling of potentially clinically significant ECG readings, as defined in Section 12.8.5.	Administrative update.

Affected Sections/Tables	Summary of Revisions Made	Rationale
Table 2 Section 11.2 Section 11.3 Section 12.8.6 Appendix E	Clarified description of the assessment of the injection site, if required 24 ( $\pm 3$ ) hrs post-dose to be completed using the Modified Draize Scale.	Administrative update
Section 5.5	Updated lowest dose of XP-8121 administered to 100 $\mu$ g.	Updated the lowest dose to 100 $\mu$ g to correspond to the initiation dose required for the lowest dose of oral levothyroxine.
Section 5.5	Updated lowest daily dose of oral levothyroxine permissible for enrollment to 50 $\mu$ g.	Updated to ensure that the lowest dose of oral levothyroxine aligned with the conversion criteria being applied for the minimum starting dose of XP-8121 (eg, 4 times 50 $\mu$ g, is 200 $\mu$ g, and the 50% starting dose would be the minimum dose of 100 $\mu$ g XP-8121).
Section 8.2	Exclusion Criteria #3 updated lowest dose of oral levothyroxine permissible for enrollment to 50 $\mu$ g.	Updated to ensure that the lowest dose of oral levothyroxine aligned with the conversion criteria being applied for the minimum starting dose of XP-8121 (eg, 4 times 50 $\mu$ g, is 200 $\mu$ g, and the 50% starting dose would be the minimum dose of 100 $\mu$ g XP-8121).
Section 8.2	Exclusion Criteria #8 updated the minimum hematocrit level allowed for enrollment to 33.5% for females and 38.7% for males.	Updated to align with the normal range for the central laboratory being used for the study.
Section 8.2	Exclusion Criteria #9 updated the minimum hemoglobin level allowed for enrollment to 10.8 g/dL for females and 12.8 g/dL for males.	Updated to align with the normal range for the central laboratory being used for the study.
Section 9.1	Removed description of unit markings on syringe.	Administrative update.
Section 11.2	Clarified timing of urine pregnancy test during Titration Period as Weeks 1, 3, 5 and 7. Removed clinical safety laboratory assessments from the end of the Titration Period.	Administrative update.
Section 11.3	Added clinical safety laboratory assessments to the beginning of the Maintenance Period	

Affected Sections/Tables	Summary of Revisions Made	Rationale
Section 11.2.1 Table 6 Table 7	Updated volume of blood drawn in the Titration and Maintenance Periods.	Updated to align with the shift of clinical laboratory assessments from the end of the Titration Period to the beginning of the Maintenance Period, maximum total volume remained unchanged. Updated to clarify minimum volume requirements for minimum free and total T4 sample collections.
Appendix C	Clarified question to align with the qualitative nature and duration of the potential discomfort associated with the delivery of study drug.	Administrative clarification.

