### 12.8.6. Local Tolerability

Local tolerability will be assessed following SC injection as follows:

- The Investigator/qualified designee will use the Modified Draize Scale ([Appendix E](#)) to assess erythema and edema formation at the injection site at  $30\pm5$  minutes after injection of XP-8121. Note: If the Draize score is  $>1$  at 30 minutes, the subject will be discharged, and a follow up visit will be scheduled at 24 ( $\pm3$ ) hrs after injection in order for the Investigator or designee to complete an assessment of the injection site using the Modified Draize Scale.

- To assess injection site discomfort, subjects will complete an 11-point Numeric Rating Scale (NRS) questionnaire and an Injection Site Discomfort Description and Duration Questionnaire 10 ( $\pm 2$ ) minutes after injection of XP-8121 ([Appendix C](#)).

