6.9.7 Local Tolerability

Local tolerability will be assessed using the Modified Draize Scale and Injection Site Discomfort questionnaires following protocol-specified timepoint following SC injections of XP-8121. The Modified Draize Scale assesses Erythema and Edema on a 0 to 4 point scale with 0 being None and 4 being Severe.

Injection site discomfort will be assessed using an 11-point Numeric Rating Scale (NRS) and an Injection Site Discomfort Description and Duration Questionnaire following injection of XP-8121. Injection Site Discomfort Intensity will be categorized into the following groups: Mild = 1 – 3, Moderate = 4 – 6, and Severe = 7 – 10.

Time until onset of discomfort (minutes) and Duration of discomfort (minutes) will be summarized as reported on the eCRF.

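### The erythema score-2 descriptor in Appendix E requires raised edges, so flat, visible redness can be scored 1, 2 or 3 at the cut that triggers the 24-hour recheck

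*Protocol*

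**What the plan says.** Protocol Appendix E gives a two-column table with scores 0 to 4 for erythema and, separately, for edema. Its instructions state: "The injection site should be examined by the Investigator/qualified designee for formation of both erythema and edema". At score 2 both columns carry the same descriptor, "Edges of area well defined by definite raising", one under the label of slight erythema and the other under slight edema.

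Protocol section 12.8.6 sets the action rule. If the score exceeds 1 "at 30 minutes, the subject will be discharged, and a follow up visit will be scheduled at 24" (±3) hours after injection, so that the site can be rated again. The same rule stands in Table 2 (footnote p), sections 11.2 and 11.3, and Appendix E.

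The scale is listed with the tolerability assessments among the primary endpoints (Protocol 13.5.1, SAP 6.6). Protocol 13.7.4 and SAP 9.8.7 tabulate the number and percentage in each grade, and SAP 9.8.7 adds means and standard deviations. SAP 6.9.7 says only this about the grades: "The Modified Draize Scale assesses Erythema and Edema on a 0 to 4 point scale", naming the two end points and nothing between them.

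**The concern.** Raising describes swelling. As the descriptor of an erythema grade, it asks the rater to judge redness by a feature of edema. The mismatch lies at the boundary between scores 1 and 2, which is also the boundary that decides whether the 24-hour visit takes place.

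Two things are at stake. The first is the erythema grade table for a measure listed as primary, in a multicenter open-label study whose protocol and SAP describe no rater training or central reading for this scale. The second is consistent use of the recheck rule: two raters looking at the same site could reach different decisions about the follow-up visit.

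**Working it through.** There is no stated figure to reproduce. The check is a reading of the table grade by grade, followed by a search for text elsewhere that would settle the matter.

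**The two columns side by side (Protocol Appendix E)**

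| Score | Erythema descriptor | Edema descriptor |
|---|---|---|
| 0 | none present | none present |
| 1 | "Barely perceptible" | "Barely perceptible" |
| 2 | "Edges of area well defined by definite raising" | "Edges of area well defined by definite raising" |
| 3 | label only: "Moderate erythema" | "Raised approx. 1 mm" |
| 4 | "Beet redness to slight eschar formation" | more than 1 mm high and spreading past the exposure area |

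In the edema column, scores 2, 3 and 4 form one progression in height. In the erythema column, scores 1 and 4 describe how visible or how red the site is, score 3 has no descriptor, and only score 2 refers to height. The phrase appears complete in both cells, each with its own label and score, so it does not look like a broken table.

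**Case A: flat, plainly visible redness, not beet red, no swelling (edema 0)**

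- Score 0 is excluded, because redness is present.
- Score 1 conflicts with its descriptor, because the redness is more than barely visible.
- Score 2 fits the label and fails the descriptor, because nothing is raised.
- Score 3 has nothing in the table to exclude it.
- Score 4 is excluded.

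A rater who gives most weight to the missing raising gives 1. One who goes by the label gives 2. One who rejects both descriptors gives 3. With edema at 0, the higher of the two scores and their sum coincide: 1 + 0 = 1 (no recheck), 2 + 0 = 2 (recheck), 3 + 0 = 3 (recheck). The recheck then depends on the rater's choice.

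**Case B: definite raising with barely perceptible redness**

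Edema is at least 2. Erythema is 1 by visibility, or 2 if the rater follows the score-2 descriptor. Whether the trigger uses the higher score or the sum, edema alone exceeds 1 and the recheck follows. Only the erythema count moves.

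**Does any other text settle it?** Protocol Table 2 (footnote p) and sections 11.2, 11.3, 12.8.6 and 13.7.4, and SAP 6.9.7 and 9.8.7, all refer to the scale. None defines erythema score 2 differently.

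**How many ratings use the table?** At most 8 weekly titration doses plus 4 maintenance doses gives 12 injections per subject, and 12 × 44 = 528 ratings at 30 minutes. This is the ceiling on use of the table. It does not estimate how many scores would change, and the documents give no figure for the share of reactions that are flat but clearly visible.

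**The case against.** The strongest reply is that each row has a label as well as a descriptor. Flat, visible redness can be scored 2 by its label, or 3, which has no descriptor to contradict. Both exceed 1 and trigger the recheck. To miss it, the rater must call plainly visible redness barely perceptible, which also departs from the table, and raters are investigators or qualified designees. This stands. A reader might infer that such redness has no grade at all, or that the recheck will certainly be missed. The table does not support either reading. It supports inconsistency, with the direction of error unknown.

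A reader might also infer that a raised lesion is counted twice. The documents do not support that: the two columns are scored and reported separately, and no summed score is defined for analysis.

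The site is also seen in other ways. The protocol allows unscheduled safety assessments and records observed adverse events. Abbreviated examinations, which include skin, take place at the weekly titration visits and at 72 hours (±1 day) after the initial dose and each up-titration. This softens the safety consequence, though less so at the maintenance dosing visits, where Table 2 schedules no physical examination.

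Finally, Appendix E cites two sources for the scale that are not available here. The phrase may be a slip, a faithful copy or a deliberate modification. The documents cannot settle which, so the finding rests on the table's inconsistency with itself.

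**Conclusion.** The point holds as an internal inconsistency in one cell of a scoring table. Erythema score 2 is described by the edema dimension, at the cut that triggers the 24-hour reassessment, and no other text resolves it. The effect is that raters may score the same flat, visible redness as 1, 2 or 3, which makes both the erythema category counts and the recheck trigger inconsistent.

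The size is limited. One of five erythema grades is affected, the share of scores that would differ is unknown, and the maximum of 528 ratings must not be read as an effect. The measure is listed as primary, but Protocol 13.7 plans no hypothesis test on safety data, and the dose conversion factor, which drives the sample size, is untouched. The consequences are confined to descriptive local-tolerability tables and the recheck visit.

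The conclusion assumes that raters work from the Appendix E table, and that no separate manual or eCRF text gives a different descriptor.

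**What to change.** In Appendix E, replace the erythema score-2 descriptor with one based on redness that does not require raising. Verify the wording against the sponsor's cited source scale. Keep the raising phrase in the edema column only. Make the same change in the eCRF if it carries the same text, and send raters the corrected table.

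If scores have already been collected with the present descriptor, state in the study report which descriptor was in use and list erythema scores by descriptor version. Collapsing erythema to 0–1 against 2–4 would not rescue those data, because that split falls on the boundary in question.

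The cost is one table cell, a possible eCRF edit and a memo to raters. There are two downsides: scores before and after the change are not strictly comparable, and there may be a few more 24-hour rechecks.

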2.0	04APR2024		
Section 6.5: Clarified the prior medication definition to only include medications which were discontinued prior to treatment.
 
Section 6.7: Wording clarification, no change to methods
 
Sections 6.9.1 and 9.8.1: Corrected the XP-8121 dose volume to be μL rather than mL.
 
Section 6.9.5: Described handling of triplicate values for clarification. Adjusted wording for clinically significant vital signs to be per EDC not investigator's discretion.
 
Section 6.9.5 & 9.8.5: Removed BMI from change from baseline summary since it is only collected at baseline.
 
Section 8.3: Added requirement that no date imputation will be done for medications marked as "Ongoing"
 
Section 9.5: Removed statement of primary hypothesis. Added figure relating dose conversion factor to prior oral levothyroxine dose. Clarified difference between the general dose conversion factor and the final dose conversion factor. Added scatterplot of dose conversion factor over time. Added requirement to perform sensitivity analyses only if not all subjects have primary hypothyroidism
 
Section 9.6: Scatterplot updated to be box plot
 
Section 9.8.1: Scatterplot removed

TABLE OF CONTENTS

1. List of Abbreviations	6
2. Introduction	7
2.1 Hypothyroidism.....	7
2.2 Study Design and Dose Range Rationale	7
3. Study Objectives.....	8
3.1 Primary Objectives	8
3.2 Secondary Objectives.....	8
3.3 Exploratory Objectives.....	8
4. Study Design	9
4.1 General Design	9
4.2 Randomization and Treatment Assignments.....	10
4.3 Blinding/Unblinding	10
4.4 Sample Size Considerations	10
5. Changes in the Analyses Specified in the Protocol.....	10
6. Study Endpoints	10
6.1 Schedule of Assessments	10
6.2 Timepoint Definitions	11
6.2.1 Relative Day	11
6.2.2 Visit and Timepoint Windows	11
6.2.3 Baseline	11
6.3 Protocol Deviations.....	11
6.4 Demographics and Baseline Characteristics	11
6.5 Prior and Concomitant Therapies	12
6.6 Primary Endpoints.....	12
6.7 Secondary Endpoints	13
6.8 Exploratory Endpoints.....	13
6.9 Safety Endpoints	15
6.9.1 Study Drug Exposure and Compliance	15
6.9.2 Adverse Events.....	16
6.9.3 Clinical Laboratory Assessments.....	16
6.9.4 Electrocardiograms	16
6.9.5 Vital Signs	16

6.9.6	Physical Examination.....	17
6.9.7	Local Tolerability	17
7.	Analysis Sets.....	17
8.	Statistical Methods.....	18
8.1	General Methodology	18
8.2	Adjustments for Covariates	18
8.3	Handling of Dropouts or Missing Data.....	18

1. LIST OF ABBREVIATIONS

Abbreviation or Term	Definition
ATC	Anatomical Therapeutic Chemical
AUC	Area under the concentration vs. time curve
BMI	Body mass index
C	Celsius
CI	Confidence Interval
cm	Centimeter
C_{min}	Minimum observed concentration
C_{max}	Maximum observed concentration
CS	Clinically Significant
CRU	Clinical Research Unit
CTMS	Clinical Trial Management System
C_{ss}	Mean concentration at steady state
C_{trough}	Last concentration
%CV	Coefficient of variation
DBP	Diastolic blood pressure
ECG	Electrocardiogram
eCRF	Electronic Case Report Form
ET	Early Termination
FDA	United States Food and Drug Administration
fT4	Free Thyroxine
ms	milliseconds
MedDRA	Medical Dictionary for Regulatory Activities
PK	Pharmacokinetic
PO	Oral
PT	Preferred Term
QTcB	QT interval using Bazett's formula
QTcF	QT interval using Fridericia's formula
SBP	Systolic blood pressure
SC	Subcutaneous
SD	Standard Deviation
SOC	System Organ Class
T3	Triiodothyronine
T4	Thyroxine
TEAE	Treatment-Emergent Adverse Event
t_{max}	Time to occurrence of C_{max}
TSH	Thyroid Stimulating Hormone
TSQM-9	Treatment Satisfaction Questionnaire for Medication
WHO	World Health Organization
Xeris	Xeris Pharmaceuticals, Inc.

2. INTRODUCTION

Xeris Pharmaceuticals, Inc. (Xeris) has developed a novel formulation of levothyroxine, XP-8121 (levothyroxine sodium for subcutaneous [SC] injection) to mitigate challenges associated with oral (PO) formulations of levothyroxine, which can include interference with absorption (e.g., simultaneous ingestion with calcium, iron, certain foods, other drugs, and conditions that impair gastric acidification or intestinal absorption, such as celiac disease). For this reason, subjects are usually instructed to ingest oral levothyroxine on an empty stomach 30 to 60 minutes before food intake. Further, a once weekly dosing schedule, as provided by XP-8121, could improve adherence that is adversely affected by unintentionally missed daily doses. Finally, SC administration of XP-8121 could alleviate burdens associated with swallowing difficulties or other barriers to taking daily medication.

2.1 Hypothyroidism

The thyroid gland is responsible for the synthesis, storage, and release of the thyroid hormones, thyroxine (T4) and triiodothyronine (T3) [Colucci et al, 2013]. These hormones are nuclear receptor-activating and regulate critical metabolic processes that are vital for normal growth, development, and health throughout life.

Deficiency of circulating T4 or T3 is known as hypothyroidism. Most commonly in developed countries, the primary cause of hypothyroidism is autoimmune destruction of the glands responsible for thyroid hormone synthesis, also known as Hashimoto's disease or autoimmune thyroiditis. Other causes of primary hypothyroidism (thyroid hormone production/release deficits) include other forms of thyroid inflammation and iatrogenic causes (surgery and radiation sequelae and certain medications, iodine deficiency, et al). Uncommonly, thyroid synthesis is impaired at birth (congenital). Hypothyroidism can also result from problems with Thyroid Stimulating Hormone (TSH) production/secretion or action (secondary hypothyroidism, most commonly because of pituitary tumor or trauma) or from hypothalamic dysregulation of pituitary function (tertiary hypothyroidism). Rare syndromes of resistance to the actions of thyroid hormone can also resemble more typical hypothyroidism [Laurent et al, 2018; Colucci et al, 2013; Winther et al, 2016].

Regardless of etiology, inadequate thyroid hormone that manifests clinically should be treated, i.e., thyroid hormone replacement. Treatment is often chronic, most commonly lifelong. The goal of replacement therapy is restoration of the euthyroid state, with reversal of the clinical manifestations of hypothyroidism. In most developed countries, replacement most commonly consists of levothyroxine monotherapy and in most guidelines, TSH is currently recommended as the sole biomarker of replacement adequacy.

2.2 Study Design and Dose Range Rationale

The current study was designed, incorporating United States Food and Drug Administration (FDA) guidance, to provide information on weekly use of XP-8121 in stably treated subjects with hypothyroidism. XP-8121 is a ready-to-use, liquid formulation of levothyroxine sodium intended for SC administration once-weekly. The goals of the study are to determine safe starting doses, safe and feasible titration schedules, and the effective dose range of XP-8121, wherein effectiveness is determined by maintenance of normalized TSH. The oral to injected dose-conversion target was considered the primary objective and serves as the basis for hypothesis testing and sample size determination. Pharmacokinetics will also be characterized in a subset of subjects to determine any

differences from modeled chronic pharmacokinetic (PK) that used data from healthy volunteers. The findings from this study will inform a future clinical efficacy and safety demonstration.

This is a non-randomized, open-label, single arm, self-controlled study (i.e., subjects serve as their own controls based on baseline assessment of thyroid function). The design is appropriate because replacement of deficient T4 with levothyroxine is necessary and sufficient to treat hypothyroidism. A comparator is not necessary for an initial assessment of the ability of SC administered levothyroxine to maintain normalized TSH in stably treated subjects, as efficacy is not being established by this study. Blinding is not necessary since all subjects receive active therapy and there is no comparator. Furthermore, the primary outcome measure, TSH, is objective, and compliance (adherence) with therapy will be assessed.

The XP-8121 initiation dose will correspond to 50% of the target weekly dose of XP-8121 SC, which is defined, per study hypothesis, as the baseline daily oral levothyroxine dose (in μ g) multiplied by 4, rounded up to the nearest 50 μ g. The lowest dose to be studied is 100 μ g. The highest dose to be studied is 1500 μ g weekly, selected based on the known safety and toxicity profile of levothyroxine, published use of oral levothyroxine as a weekly dose regimen, and the observed and expected PK profile of XP-8121. This dose is not expected to result in overdosage using the proposed biweekly titration-to-target scheme with careful safety monitoring as described below.

